6.10. Bone Evaluations

In a subset of participants (except in Germany), DXA scans of the hip and spine will be performed throughout the study.

During the blinded phase of the study, all DXA substudy participants will have scans at Day 1, Week 48, Week 96, and end of blinded treatment phase visits. CCI

The Day 1 scan must be completed \pm 14 days from start of treatment. All other scans should be completed \pm 6 weeks of the protocol-specified visit date.

DXA substudy participants who plan to temporarily interrupt study drug for more than 14 days should have the DXA scans performed within 14 days of the last dose of study drug, unless the participant has had scans performed for a Week 48, Week 96, end of blinded treatment Phase. CCI

DXA scans will be completed at the ESDD visit if the ESDD visit is $>$ 12 weeks after the previous DXA scan. Participants who have permanently discontinued study drug will not have DXA scans performed during subsequent study visits.

DXA scans will cover the spine and hip to measure changes in BMD. DXA scan results will be provided to study sites as they become available.

A complete description of the procedures performed for the DXA scans will be provided in a DXA manual.

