In a subset of approximately 400 subjects at a subset of sites (excluding Germany), DXA scans are performed prior to or within 14 days of the start of study treatment, and then at Week 48, Week 96, the End of Blinded Treatment Phase visit, OL Week 48, and Early Study Drug Discontinuation Visit, if > 12 weeks from the prior DXA scan.

More details for study procedures could be found in Appendix 1.

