## 3.1.5. DXA Analysis Sets

# 3.1.5.1. Hip DXA Analysis Set

The **Hip DXA Analysis Set** will include all subjects who (1) are in the Safety Analysis Set and (2) have nonmissing baseline hip BMD values. Subjects will be grouped according to the treatment they actually received.

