# 3.8. Analysis Windows

# 3.8.1. Definition of Study Day

**Study Day 1 (DB phase)** is defined as the day when the first dose of randomized study drug (ie, *F/TAF or Placebo-to-match F/TAF*, *F/TDF or Placebo-to-match F/TDF*) was taken, as recorded on the Study Drug Administration eCRF form.

**Study Day 1 (OLE phase).** For subjects who were treated in the OLE phase, Study Day 1 is defined as the day when the first dose of OLE phase study drug (ie, F/TAF) was taken, as recorded on the "Extension Phase" Study Drug Administration eCRF.

**Study Days** are calculated relative to Study Day 1 for each phase. For events that occurred on or after the Study Day 1 date, the number of study days is calculated as (visit date minus Study Day 1 date plus 1). For events that occurred prior to DB phase Study Day 1, the number of study days is calculated as (visit date minus Study Day 1 date).

**Last Dose Date (DB phase)** is the latest of the blinded study drug end dates (administering ≥1 tablet per day) recorded on the Study Drug Administration eCRF form with "Permanently Withdrawn" box checked for subjects who prematurely discontinued or completed study drug in the blinded treatment study phase according to the Study Drug Completion eCRF.

If last dose date is completely missing (ie, due to lost to follow-up) for subjects who prematurely discontinued or completed blinded study drug at the data cut date in the DB phase, the latest of study drug start dates and end dates, the clinic visit dates, and the laboratory visit dates excluding the date of 30-day follow-up visit, from the DB phase data, will be used to impute the DB phase last dose date. For other partial missing last dose date, please see the programming specifications for imputation rule details.

If the DB phase last dose date is after the first dose date of the OLE phase, use the day before the first dose date of the OLE phase to impute it.

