Last Dose Date (OLE phase) is defined as the latest of the OLE phase study drug end dates recorded on the "Extension Phase" Study Drug Administration eCRF with "Permanently Withdrawn" box checked for subjects who prematurely discontinued study drug according to the "Extension Phase" Study Drug Completion eCRF. This date will only be available for subjects treated in the OLE phase of the study. If the last dose date is missing for subjects who prematurely discontinued study drug in the OLE phase of the study, the latest of nonmissing OLE phase study drug start dates and end dates, the clinical visit dates, and the laboratory visit dates, excluding the date of 30-day follow-up visit, from the OLE phase data, will be used to impute the OLE phase last dose date.

**Last Study Date** is the latest of the randomized or OLE phase (if available) study drug start dates and end dates, the clinic visit dates, and the laboratory visit dates, including the 30-day follow-up visit date, for subjects who prematurely discontinued study or who completed study according to the Study Completion eCRF.

Last At-Risk of HIV Infection Date (DB phase) is (1) the date of HIV infection diagnosis as defined in Section 6.2.2 for subjects who have been diagnosed as infected with HIV during the DB phase or (2) the date of the last post-baseline HIV laboratory test (either local rapid or Covance HIV laboratory tests, including the 30-day follow-up visit date) during the DB phase for subjects who have not been infected with HIV during the DB phase.

Last At-Risk of HIV Infection Date (OLE phase) is (1) the date of HIV infection diagnosis as defined in Section 6.2.2 for subjects who have been diagnosed as infected with HIV during the OLE phase or (2) the date of the last post-baseline HIV laboratory test (either local rapid or Covance HIV laboratory tests, including the 30-day follow-up visit date) during the OLE phase for subjects who have not been infected with HIV.

**Baseline value** is defined as the last value obtained on or prior to Study Day 1 for each phase for all assessments, except for DXA BMD. The baseline value for DXA BMD is defined as the last value obtained on or prior to Study Day 14 of each phase.

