- q At Screening, if HIV 1 Ab/Ag is positive the subject is a screen failure. At all other visits if HIV 1 Ab/Ag is positive, then HIV 1 RNA by PCR test and sample collection for possible genotypic testing will be completed.
- At Screening or Day 1, if the subject has a negative rapid test, but has signs or symptoms of acute HIV 1 infection, an HIV 1 RNA by PCR test will be completed and if HIV 1 RNA by PCR is positive, subject cannot participate in the study. At all other visits, HIV 1 RNA by PCR and sample collection for possible genotypic resistance testing will be completed for any subjects who (1) have a positive retest rapid HIV 1 Ab/Ag test or (2) have a positive HIV 1 Ab/Ag test or (3) show symptoms consistent with acute infection regardless of the results of the rapid tests, (4) have a recent exposure that is considered high risk for HIV infection, or (5) have been confirmed HIV infected. If HIV infection is confirmed, subject will discontinue study drug immediately and should return for an ESDD visit within 72 hours. The subject will receive counseling and be referred for appropriate care. If viral load > 400 copies/mL the collected sample will be sent for genotypic resistance testing.
- s At Day 1, HIV 1 RNA by PCR and sample collection for possible genotypic testing will be completed for any subjects who show symptoms consistent with acute HIV 1 infection regardless of the results of the rapid tests.
- t Every 24 Weeks only.
- u Only risk reduction counseling at Screening.
- v DXA scans of hip and spine in substudy participants (within 14 days prior to or after the start of treatment).
- w DXA scans are to be scheduled ± 6 weeks to the protocol specified dates for the Week 48, Week 96, End of Blinded Treatment Phase, and OL Week 48 visits.
- x DXA scan of hip and spine in substudy participants (if discontinuation is > 12 weeks from the prior DXA scan).
- y Only study drug dispensation at Day 1.
- z OL drug dispensation (all eligible subjects will receive F/TAF).
- aa Study drug dispensing: No study drug dispensation at OL WK 48 except for subjects continuing on past OL WK 48 due to commercial drug unavailability.
- ab No study drug dispensed.
- ac Swabs may be self administered by the subject at the discretion of the investigator.
- ad Hepatitis B testing (HBsAg, HBsAb, HBcAb) to be completed every 24 weeks. Hepatitis B testing to be completed at the End of Blinded Treatment Phase visit if > than 24 weeks from prior testing.

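### The SAP's DXA baseline window closes one day before the permitted baseline scan window does, so a compliant scan 14 days after first dose would not count as baseline

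*SAP*

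**What the plan says.** Three places define when the baseline scan may be done. Protocol 6.10 says: "The Day 1 scan must be completed \pm 14 days from start of treatment", that is, from 14 days before to 14 days after. SAP 1.2 (Schedule of Assessments) says: "DXA scans are performed prior to or within 14 days of the start of study treatment". Footnote v to the SAP study procedures table (Appendix 1) gives the same limits: "within 14 days prior to or after the start of treatment".

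SAP 3.8.1 sets the day count. Study Day 1 "is defined as the day when the first dose of randomized study drug" was taken, and for dates on or after it "the number of study days is calculated as (visit date minus Study Day 1 date plus 1". There is no Day 0.

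SAP 3.8.1 then fixes the analysis baseline: "The baseline value for DXA BMD is defined as the last value obtained on or prior to Study Day 14 of each phase". Table 3-5 and its note repeat this, with a baseline upper limit of Day 14 and a Week 48 window of Days 15 to 504.

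Entry to the Hip DXA Analysis Set (SAP 3.1.5.1) requires that participants "have nonmissing baseline hip BMD values". SAP 3.1.5.2 sets the same condition for spine.

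**The concern.** The number 14 is used in two ways. In the scan window it counts days elapsed since first dose. In the analysis window it is a Study Day, which is one larger than the days elapsed. The analysis baseline therefore ends 13 days after first dose, and the last compliant scan date falls outside it. The SAP conflicts with its own 1.2 and Appendix 1 here, as well as with the protocol.

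A participant scanned for the first time on that date has no baseline value, so no percentage change in BMD can be computed at Week 48, Week 96 or later, even if every later scan is valid. BMD is measured in only about 400 participants, and hip and spine BMD at Week 48 are the first two endpoints in the alpha-controlled sequence (protocol 8.6). A compliant measurement should not be lost to a counting convention.

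**Working it through.** **Inputs.** Permitted scan window: 14 days before to 14 days after first dose (protocol 6.10; SAP 1.2; SAP Appendix 1, footnote v). Study-day formula and baseline limit: SAP 3.8.1. Analysis windows: SAP Table 3-5. Substudy size of 200 per arm, difference of 1.54%, SDs of 3.05% and 3.15%, two-sided level 0.01: SAP 1.3.1.

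**Step 1: assign the permitted dates.** On or after first dose, Study Day = days since first dose + 1. Before first dose, Study Day = the plain date difference.

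| Days from first dose | Study Day | Table 3-5 window |
|---|---|---|
| -14 | -14 | Baseline |
| 0 | 0 + 1 = 1 | Baseline |
| +13 | 13 + 1 = 14 | Baseline |
| +14 (last permitted) | 14 + 1 = 15 | Week 48 |

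Only +14 is misassigned. Without the + 1 the two limits would agree, but the SAP formula includes it.

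**Step 2: look for a rule that rescues the scan.** None was found. SAP 3.8.3 gives the general baseline rule as on or before first dose unless specified otherwise, which would not admit a Day 15 scan either. The LOCF and BlOCF sensitivity analyses (SAP 7.3.1) use the same DXA sets, and carrying a baseline forward requires one. SAP 7.8 lists the deliberate change to the DXA sets, which drops the requirement for a postbaseline value. It does not mention a shorter baseline window.

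**Step 3: see what happens in the Week 48 window.** A true Week 48 scan displaces the Day 15 scan under either selection rule: closest to nominal Day 336 (SAP 3.8.2) or latest in the window (SAP 3.8.3). Those two rules differ from each other, but not on this point.

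**Step 4: size.** The documents give no distribution of scan dates, so these are assumptions:
- No scan on day +14: 0 of 400.
- 20% of scans after first dose, spread evenly over 14 days: 400 × 0.20 / 14 = 5.7, about 6 of 400.
- All scans spread evenly over 14 + 1 + 14 = 29 days: 400 / 29 = 13.8, about 14 of 400 (3.4%).

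**Step 5: power.** Common SD = √((3.05² + 3.15²)/2) = 3.10. Power ≈ Φ(1.54 / (3.10 × √(2/n)) − 2.576), with n per arm.
- n = 200: Φ(4.97 − 2.58) = 99.2%, consistent with the SAP's claim of at least 95%.
- n = 193 (even spread, 200 − 200/29): 98.9%.
- n = 180 (an arbitrary 10% loss): 98.4%.

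**The case against.** The best reply is that nothing in the documents shows a single scan on day +14. In the SAP schedule the baseline DXA sits in the Day 1 column, so clustering near Day 1 is at least as plausible as an even spread, and the count may be zero. Assignment is randomized and double-blind, so there is no evident reason for late baseline scans to differ by arm. This stands: the loss has to be stated conditionally, and no bias mechanism is apparent.

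A second reply is that analysis windows need not match scheduling windows. The protocol allows ±6 weeks around the Week 48 scan, while Table 3-5 uses Days 15 to 504. That is true, but there the analysis window is wider and keeps compliant scans. Here it is narrower and excludes one.

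A third reply concerns timing. The primary analysis has been reported (SAP 1), Week 48 BMD is an alpha-controlled endpoint, and SAP 3.1 asks for inclusion rules to be settled before the blind is broken. The primary analysis SAP is not among the documents. If it used the same limit, changing the limit now could make Week 48 BMD results differ between reports. In addition, baseline is the last value in the window, so simply extending it would let a Day 15 repeat scan replace a pre-dose baseline. Both points stand and shape the fix.

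A reader might infer that participants are dropped from the study, or that Week 48 data are contaminated. Neither follows. Exclusion is from the two DXA sets only, and applies only without a scan by Study Day 14. A real Week 48 scan displaces the Day 15 one, and without a baseline there is no percentage change to contaminate.

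**Conclusion.** The mismatch holds as a matter of counting. The last permitted baseline scan date is Study Day 15, and the SAP ends DXA baseline at Study Day 14. A participant with no scan on or before Study Day 14 and a compliant scan on day +14 would be lost from every hip and spine BMD comparison.

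The size is unknown and probably small. One permitted day in 29 is affected. The figure of about 14 of 400 rests wholly on a hypothetical even spread, and zero is equally compatible with the documents. Even with that loss power is about 98.9%, against 99.2% with none. The documents therefore do not support a stronger reading, that the BMD comparisons are underpowered or biased or that participants were in fact lost. This is a low-severity correction that makes the SAP consistent with the protocol and with itself.

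**What to change.** Before database finalization, make these changes for the double-blind phase:

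- In SAP 3.8.1, Table 3-5 and the table's note, set the DXA baseline upper limit to Study Day 15, written also as first dose date + 14 days. Start the Week 48 window at Day 16.
- State that a Day 15 scan serves as baseline only when there is no scan on or before Study Day 14, so that no existing baseline value changes.
- Report by arm how many participants are reclassified. Record the change in SAP 7.8 or the revision table, and note any resulting difference from the Week 48 BMD results in the primary analysis report.

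The cost is a few text edits, one window parameter with a precedence rule, and one reported count. There are no new procedures for participants. If no scan falls on Study Day 15, the change alters no result.

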# 3.8.2. Analysis Windows

Subject visits might not occur on protocol specified days. Therefore, for the purpose of analysis, observations collected from the DB phase of the study (ie, DB phase data) will be assigned to analysis window. Observations collected from the OLE phase of the study (ie, OLE phase data) will not have analysis window assigned and will be included in listings with derived visit marked as "Extension".

The CASI questionnaire assessment consists of different versions of the questionnaire corresponding to 3 different time periods: screening, baseline and follow-up. All versions of the CASI questionnaire include questions regarding number of sexual partners. For the CASI Screening questionnaire items regarding the number of sexual partners in the last 90 days, the analysis windows are defined as prior to the first dose date. For the CASI Baseline questionnaire items, the analysis windows are defined up to or on the first dose date.

Aside from the number of sexual partners, other items collected in the CASI Screening questionnaire are unique to the screening questionnaire and collected only once (including education, circumcision, drug use, management of HIV risk, etc.) All of these other CASI Screening questionnaire items will be summarized for the Screening visit without applying an analysis window.

The analysis windows for HIV, hematology, chemistry (including glucose), urinalysis, renal biomarkers, eGFRCG, vital signs, weight, CASI Follow-Up questionnaire, and DBS are presented in Table 3-1.

Table 3-1. Analysis Windows for HIV, Hematology, Chemistry, Urinalysis, Renal Biomarkers, eGFRCG, Vital Signs, Weight, CASI Follow-Up Questionnaire, and DBS

Visit ID	Nominal Day	Lower Limit	Upper Limit
Baseline	1	(none)	1
Week 4	28	2	56
Week 12	84	57	126
Week 24	168	127	210
Week 36	252	211	294
Week 48	336	295	378
Week 60	420	379	462
Week 72	504	463	546
Week 84	588	547	630
Week 96	672	631	714
Week 108	756	715	798
Week 120	840	799	882
Week K (K is every 12 weeks after previous visit)	K*7	(K-6)*7+1	(K+6)*7

HIV laboratory tests include both Covance central laboratory tests (HIV antibody screening tests, HIV Antibody Supplemental tests, qualitative and quantitative tests) and local laboratory tests (rapid HIV 1 Ag/Ab test or other local laboratory tests collected from eCRFs).

CASI follow up questionnaire collected at post baseline visits only, no baseline analysis window will be applied.

The analysis windows for fasting glucose, lipids (including total cholesterol, high density lipoprotein [HDL], direct low density lipoprotein [LDL], and triglycerides), HBV serology (including HBsAb, HBsAg, and HBcAb) and HBV DNA assessments are presented in Table 3-2.

Table 3-2. Analysis Windows for Fasting Glucose, Lipids, HBV Serology and HBV DNA Assessments

Visit ID	Nominal Day	Lower Limit	Upper Limit
Baseline	1	(none)	1
Week 24	168	2	252
Week 48	336	253	420
Week 72	504	421	588
Week 96	672	589	756
Week 120	840	757	924
Week K (K is every 24 weeks after previous visit)	K*7	(K-12)*7+1	(K+12)*7

Fasting glucose and lipids (fasting not required at screening) include total cholesterol, HDL, total cholesterol to HDL ratio, direct LDL, and triglycerides from Covance central laboratory data.

The analysis windows for anytime PK, STI laboratory tests for gonorrhea, chlamydia and syphilis as well as syphilis diagnosis by the investigator are presented in Table 3-3.

Table 3-3. Analysis Windows for Anytime PK, STI Laboratory Tests and Syphilis Diagnosis by the Investigator

Visit ID	Nominal Day	Lower Limit	Upper Limit
Baseline	1	(none)	1
Week 12	84	2	126
Week 24	168	127	210
Week 36	252	211	294
Week 48	336	295	378
Week 60	420	379	462
Week 72	504	463	546
Week 84	588	547	630
Week 96	672	631	714
Week 108	756	715	798
Week 120	840	799	882
Week K (K is every 12 weeks after previous visit)	K*7	(K 6)*7+1	(K+6)*7

STI laboratory tests include Covance central laboratory tests and local laboratory tests for gonorrhea and chlamydia (urine, rectal swab and pharyngeal swab) as well as syphilis.

The analysis windows for HCV antibody (HCVAb) and HCV RNA are presented in Table 3-4.

Table 3-4. Analysis Windows for HCV Serology and HCV RNA Assessments

Visit ID	Nominal Day	Lower Limit	Upper Limit
Baseline	1	(none)	1
Week 48	336	2	504
Week 96	672	505	840
Week K (K is every 48 weeks after previous visit)	K*7	(K-24)*7+1	(K+24)*7

The analysis windows for DXA BMD are presented in Table 3-5. Subjects will have a DXA scan at the end of blinded treatment visit, in additional to the regular DXA scans at every 48 weeks, which may result in multiple assessments for a single analysis window. For post Week 144 visit, the value closest to the lower limit of its analysis window will be used for analysis. For other visits, values closest to the nominal visit will be used.

Table 3-5. Analysis Windows for DXA BMD

Visit ID	Nominal Day	Lower Limit	Upper Limit
Baseline	1	(none)	14
Week 48	336	15	504
Week 96	672	505	840
Week 144	1008	841	1176
Post Week 144	(none)	1177	(none)

Note: The baseline value of DXA BMD is defined as the last value obtained on or prior to Study Day 14. For post Week 144, the value closest to the lower limit of its analysis window will be used for analysis.

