# The algorithm for LOCF is as follows:

- If a postbaseline value is missing in an analysis visit window, the missing value will be replaced with the last on-treatment value (ie, data collected up to 30 days after permanent discontinuation of study drug or all available data for subjects who were still on study drug) observed before the analysis visit window that has the missing value.
- Baseline values will be carried forward to impute the postbaseline value at a specific visit, if there is no nonmissing postbaseline observation collected prior to that visit.

The algorithm for BlOCF is as follows:

• Baseline values will be carried forward to impute the missing postbaseline value at a specific visit.

For missing or incomplete last dosing date of study drug, imputation rules are described in Section 3.8.1. For missing or incomplete start or end dates of study drug for the computation of study drug interruptions, imputation rules are described in Section 4.2.2.2. The handling of missing or incomplete dates for AE onset is described in Section 7.1.5.2, and for prior and concomitant medications in Section 7.6. Imputation rules for missing DBS concentration at the time of HIV diagnosis are as described in Appendix 9.

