### 7.3.1. Percentage Change from Baseline in Hip and Spine Bone Mineral Density

Percentage change from baseline in hip and spine BMD at Week 48 using observed on-treatment data are 2 of the 6 key (α-controlled) secondary endpoints.

The percentage change from baseline in hip BMD and spine BMD will be summarized for on-treatment data (ie, data collected up to 30 days after permanent discontinuation of study drug or all available data for subjects who were still on study drug) using observed data by treatment group and visit using descriptive statistics for subjects in the Hip and Spine DXA Analysis Sets, respectively, and compared between the 2 treatment groups at each visit using ANOVA, which includes baseline F/TDF for PrEP and treatment as fixed effects.

As a sensitivity analysis, hip BMD and spine BMD based on on-treatment data using the LOCF and BIOCF methods will be summarized using the Hip and Spine DXA Analysis Sets.

Median (Q1, Q3) and mean (95% CI) of the percentage change from baseline in hip BMD and spine BMD over time using observed data will be plotted by treatment group. Listings of hip and spine DXA results will be provided.

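### The Week 48 DXA window opens the day after baseline closes, so early-stop scans can count as observed Week 48 BMD, LOCF and BlOCF coincide there, and the baseline limit is one day short

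*SAP*

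**What the plan says.** **Endpoint.** SAP 7.3.1 names "Percentage change from baseline in hip and spine BMD at Week 48 using observed on-treatment data" as two of the six key alpha-controlled secondary endpoints. Protocol 8.6 places hip and spine BMD first and second in the fallback procedure (alpha 0.02 and 0.01). SAP 7.3.1 lists LOCF and BlOCF as the sensitivity analyses.

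**Window.** In SAP Table 3-5 the Week 48 row reads "Week 48 336 15 504". The note under the table says "The baseline value of DXA BMD is defined as the last value obtained on or prior to Study Day 14". The two periods adjoin.

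**Scan schedule.** Protocol 6.10 allows scheduled post-baseline scans within plus or minus "6 weeks of the protocol-specified visit date". It adds off-schedule scans. One is at early study drug discontinuation (ESDD): "DXA scans will be completed at the ESDD visit if the ESDD visit is $>$ 12 weeks after the previous DXA scan". The other is before a planned interruption of more than 14 days. After a permanent stop: "Participants who have permanently discontinued study drug will not have DXA scans performed during subsequent study visits". For baseline: "The Day 1 scan must be completed \pm 14 days from start of treatment".

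**Imputation.** Under SAP 3.6.1, LOCF carries the last on-treatment value seen before the window with the missing value. Otherwise: "Baseline values will be carried forward to impute the postbaseline value at a specific visit, if there is no nonmissing postbaseline observation collected prior". BlOCF always carries baseline.

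**Choice among several scans.** SAP 3.8.2 takes the value closest to the nominal visit (except after Week 144). SAP 3.8.3 takes the latest day in the window.

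**The concern.** The result reported as observed at Week 48 can include participants who stopped drug months earlier and whose only post-baseline scan was taken at that stop. For them the observed analysis already does what a carry-forward analysis would do, although it is not labelled so.

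A reader who sees observed, LOCF and BlOCF results side by side will take them as three views of the missing data. At Week 48 they are two, and in both of them the early scans stand as Week 48 values. This falls on the first two endpoints of the alpha-controlled family. SAP 7.8 even dropped the post-baseline requirement from the DXA analysis sets because of BlOCF, so these sensitivity analyses were meant to carry weight.

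The baseline limit raises a smaller matter: a participant scanned on a permitted day can lose their baseline.

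**Working it through.** **1. Window widths.** The nominal day is 48 × 7 = 336. The protocol's range is 336 ± 42, which is Day 294 to 378, or 85 days. Table 3-5 runs from Day 15 to 504, or 504 − 15 + 1 = 490 days. For laboratory data, including the renal endpoints of the same family, SAP Table 3-1 uses Day 295 to 378, or 84 days.

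**2. Earliest ESDD scan.** It must come more than 84 days after the previous scan. With the baseline scan between 14 days before and 14 days after first dose, the earliest is −14 + 85 = 71 to 14 + 85 = 99 days after first dose, about Week 10 to 14. SAP 7.3 accepts BMD data up to 30 days after discontinuation, so a timely ESDD scan qualifies. No scan follows it, so nothing replaces it. Pre-interruption scans have no stated 12-week minimum.

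**3. When an early scan survives selection.** A scan before Day 294 lies more than 42 days from Day 336. Any scan within the protocol's ± 6 weeks therefore replaces it under both selection rules. It survives if no later scan exists by Day 504. Under the closest-to-nominal rule it also survives if the later scan is further from Day 336, for example Day 285 against Day 390 (51 against 54 days).

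**4. LOCF against BlOCF at Week 48.** LOCF needs a post-baseline value before the window opens on Day 15. Every scan up to Day 14 is a baseline candidate, so no such value can exist. LOCF then falls back to baseline, which is the BlOCF rule. The limit on imputing before a window has closed (SAP Appendix 12, item 20) applies to both methods alike. The LOCF-minus-BlOCF difference is zero at Week 48 whatever the data. At Week 96 a Week 48 value can be carried, so the two methods differ.

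**5. The plan's power figure (SAP 1.3.1).** Inputs: 200 per arm, difference 1.54%, SDs 3.05% and 3.15%, two-sided alpha 0.01.
- Pooled SD = √((3.05² + 3.15²)/2) = 3.10.
- Standard error = 3.10 × √(2/200) = 0.310.
- Noncentrality = 1.54/0.310 = 4.97.
- Power (noncentral t, 398 df) = 99.1%, consistent with the stated minimum of 95%.

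**6. Possible dilution.** The documents give no early-stop rate. Assume that a share p of Week 48 values are early scans at a mean of 27 weeks, with linear accrual: diluted difference = 1.54 × (1 − p × (1 − 27/48)).

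| p | Difference | Power |
|---|---|---|
| 5% | 1.506% | 98.8% |
| 10% | 1.473% | 98.4% |
| 15% | 1.439% | 98.0% |

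Over a wider assumed range (5% to 30% early scans carrying 75% down to 0% of the Week 48 difference), the difference runs from 1.52% to 1.08% and power from 99.0% to 81.2%. Within the combinations computed (shares of 5%, 10%, 20% and 30%), power falls below 95% only at 20% with a quarter of the effect or less, or at 30% with half or less.

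**7. Baseline limit.** SAP 3.8.1 defines study day as date minus first-dose date plus 1. A scan 14 days after first dose is Study Day 14 + 1 = 15, past the limit of 14. Protocol 6.10 and SAP 1.2 (Schedule of Assessments) both allow that scan.

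**8. The two selection rules.** Take a Week 48 scan on Day 336 and an ESDD scan on Day 450 (114 days later, so required). SAP 3.8.2 selects Day 336 and SAP 3.8.3 selects Day 450. The Week 48 value depends on which rule is programmed.

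**The case against.** The strongest defence is that wide, contiguous windows are this SAP's open convention. Table 3-4 uses Day 2 to 504 for another 48-weekly test. ESDD scans are real, on-treatment and required by the protocol, and using them reduces selection on staying on drug. That stands as a reason to keep the wide-window result. It does not make LOCF informative at Week 48.

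It is also fair that Week 48 is the first scheduled post-baseline scan. LOCF and BlOCF would agree under any window for participants without an off-schedule scan, and BlOCF against observed remains a real contrast. But participants with early scans are exactly those for whom LOCF should differ, and the window absorbs them.

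Three stronger readings are tempting and are not supported:
- *The estimate mixes exposures of 2 to 72 weeks.* Those are the window's limits. Scheduled scans fall within ± 6 weeks of Week 48, ESDD scans cannot occur before about Week 10, and pre-interruption scans are usually replaced.
- *A baseline scan on Day 15 contaminates Week 48.* If it is the only early scan, the participant has no baseline and leaves the Hip and Spine DXA sets (SAP 3.1.5).
- *The window favours F/TAF.* If the difference grows with time on drug, early scans shrink it and work against showing one. Protocol 1.1 describes bone loss on TDF as early in onset. If the loss is front-loaded, the linear model overstates the dilution.

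**Conclusion.** Two defects follow from the text with no assumption about the data. LOCF and BlOCF are identical at Week 48, so neither tests the use of early scans. The baseline limit is one day short of what the protocol permits. The use of an ESDD scan as observed Week 48 BMD is also certain under the rules. How many participants it affects cannot be known from the documents.

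The likely effect on the estimate is modest: 1.54% to about 1.51% to 1.44%, with power near 98% to 99%. This rests on assumed early stopping of 5% to 15%, a mean scan time of 27 weeks, linear accrual and 200 analysed per arm. Power would fall below the stated 95% only under much heavier stopping and a small early effect. The baseline problem is confined to participants whose only baseline scan is on the last permitted day.

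A reader might infer that the confirmatory Week 48 test is compromised. The documents do not show that. This SAP governs the end-of-blinded-phase analysis; the primary analysis was done under a separate SAP that is not among them, so its window cannot be checked. This SAP does keep the alpha-controlled label and a fallback table for Week 48 BMD, so the correction still belongs here.

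**What to change.** 1. In SAP 3.8.1 and Table 3-5, set the upper limit for the DXA baseline to Study Day 15 and start post-baseline on Day 16.
2. Keep the wide-window Week 48 result. Add a sensitivity analysis with the lower limit at Day 294 and the upper limit kept at Day 504. Let ESDD and pre-interruption scans before Day 294 enter it only through LOCF. Observed, LOCF and BlOCF can then differ. The upper limit should not be cut to Day 378: scans on Days 379 to 504 would then belong to no window, and LOCF would replace those real values with an earlier one or with baseline.
3. Reconcile SAP 3.8.2 (closest to nominal) with SAP 3.8.3 (latest day in the window) for BMD, and state one rule.

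The cost is a small SAP edit and one extra run of an existing program. The added analysis will have slightly fewer observed Week 48 values.
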